### 2.7.2 Deaths

As stated in [Section 2.7.1](#), summary for deaths will be provided by SOC, PT of death cause and treatment. Specifically, the summary tables for core part and for overall study will be provided in core part analyses using SAF. Besides, the summary tables for extension part (using OLS) and for overall study (using SAF) will also be provided in final analyses. Listing of all deaths will be provided in both core part analyses and final analyses.

### 2.7.3 Laboratory data

Laboratory data consists of hematology, biochemistry, and urinalysis measurements. Observed value, absolute change, and percent change from baseline in continuous laboratory parameters will be summarized descriptively by visit and by treatment group. Frequency table of results for categorical laboratory parameters will be presented by visit. For some parameters, only screen tests are planned. Thus, summaries of post-baseline values will not be provided. For core part analyses, the summary tables will include Day 1 visit up to Day 180 visit. For final analyses, the summary table will include Day 1 visit up to Day 360 visit.

Shift tables using the low, normal, or high classification based on the normal range will be used to compare baseline to the worst post-baseline value by treatment group and study part for hematology and biochemistry measurements. All data collected after first dose of study treatment, from scheduled, unscheduled, and premature discontinuation visits will be used. For some parameters, if only screen tests are planned and there are no scheduled post-baseline values, then the shift table will not be provided. In final analyses, OLS will be used for the shift tables of extension part data. Besides, shift tables for overall study will also be provided using SAF.

The following ranges will be used for shift tables of eGFR, fasting glucose and HbA1c

- For eGFR, the categories will be:  
Severe =  $<30 \text{ mL/min}/1.73\text{m}^2$ ;  
Moderate =  $\geq 30 \text{ to } <60 \text{ mL/min}/1.73\text{m}^2$ ;  
Mild =  $\geq 60 \text{ to } <90 \text{ mL/min}/1.73\text{m}^2$ ;  
Normal =  $\geq 90 \text{ mL/min}/1.73\text{m}^2$ .
- For fasting glucose, the categories will be  $< 100 \text{ mg/dL}$ ,  $\geq 100 \text{ mg/dL}$  to  $< 126 \text{ mg/dL}$ , and  $\geq 126 \text{ mg/dL}$ .
- For HbA1c, the categories will be  $<5.7\%$ ,  $\geq 5.7\%$  to  $<6.5\%$ , and  $\geq 6.5\%$ .

For selected laboratory tests, the number and percentage of patients meeting the clinically notable criteria at any time, considering all data collected after first dose of study treatment, from scheduled, unscheduled, and premature discontinuation visits, will be summarized by

laboratory parameter and treatment group and study part. The worst post-baseline value will be used for this analysis. In final analyses, OLS will be used for the summary of worst post-baseline value from extension part. Besides, such summary of worst post-baseline from overall study will also be provided using SAF. Notable criteria are defined in [Appendix 5.3](#). Clinically notable criteria will be considered to be met when both of the following occur:

- Post-baseline value meets the thresholds listed in [Appendix 5.3](#).
- Baseline value and any prior post-baseline values do not meet the thresholds listed in [Appendix 5.3](#).

Furthermore, the number and percentage of participants meeting notable criteria in liver function tests (LFT) will be summarized by treatment group and study part considering post-baseline data from scheduled, unscheduled, and premature discontinuation visit. LFT criteria are defined in [Appendix 5.3](#). In final analyses, OLS will be used for the summary of post-baseline value from extension part. Besides, such summary of post-baseline from overall study will also be provided using SAF.

All laboratory data will be listed by treatment group, participant, and visit/date and if ranges are available, abnormalities will be flagged.

## **2.7.4 Other safety data**

### **2.7.4.1 ECG and cardiac imaging data**

NA

### **2.7.4.2 Vital signs**

Observed values, absolute change from baseline and percentage change from baseline will be summarized descriptively for vital sign parameters (SBP, DBP and pulse) by visit and treatment group. At each assessment, average of 3 readings will be used for analysis while all 3 readings will be provided in listing. For core part analyses, the summary tables will include Day 1 visit up to Day 180 visit. For final analyses, the summary table will include Day 1 visit up to Day 360 visit.

## **2.8 Impact of COVID-19**

Below analysis about impact of COVID-19 may be performed, if needed.

The number and percentage of participants with any and each of the following COVID-19 impacted criteria will be provided for all randomized participants by treatment group and study part: (1) missed visit due to COVID-19; (2) treatment not given due to COVID-19; (3) study treatment discontinuation due to COVID-19; (4) premature study discontinuation related to COVID-19; (5) death related to COVID-19. OLS will be used for summary of extension part data in final analyses.

## **2.9 Pharmacokinetic endpoints**

[figure not shown]
NA

[figure not shown]
**2.10 PD and PK/PD analyses**

NA

**2.11 Patient-reported outcomes**

NA

## **2.14 Interim analysis**

NA

## **3 Sample size calculation**

This study is designed to randomize approximately 200 Participants (with randomization ratio of 1:1 to inclisiran and placebo arms) in order to provide adequate information to characterize the safety profile of inclisiran as well as to have sufficient power for the primary efficacy endpoint.

## **4 Change to protocol specified analyses**

NA

## **5 Appendix**

### **5.1 Imputation rules**

#### **5.1.1 Study drug**

NA

#### **5.1.2 AE date imputation**

The partially missing AE start/end date will be imputed using the Novartis ADaM Governance Board (AGB) global standard approach. Details will be provided in the study programming datasets specifications (PDS).

### 5.1.3 Concomitant medication date imputation

For LLT, the end date will be imputed using below rules.

Year missing	Set the earliest of (last visit date, date of death, analysis cutoff date)
Month missing	Set the earliest of (last visit date, 31DecYYYY, date of death, analysis cutoff date)
Day missing	Set the earliest of (last visit date, last date of reported month, date of death, analysis cutoff date)

If imputed end date is prior to start date, set the end date using start date.

For other medications, the partially missing concomitant medication start/end date will be imputed using the Novartis ADaM Governance Board (AGB) global standard approach. Details will be provided in the study PDS.

### 5.2 AEs coding/grading

The MedDRA version which will be available at the time of database lock, will be used for the coding purpose of the adverse events.

### 5.3 Laboratory parameters derivations

For laboratory measurements below the lower limit of quantification (LLQ), LLQ/2 will be used as the numeric value for the measurement. For example, if numeric result is missing in the database and character result is “< 3”, the numeric result should be treated as 3/2 = 1.5 during analysis

For fasting glucose, only measurements taken in a fasting state will be used. Baseline glucose is defined as the average of the last two non-missing fasting glucose values on or prior to Day 1. If only one non-missing fasting glucose value is available on or prior to Day 1, the available value will be used as baseline.

Notable laboratory values are defined in [Table 5-1](#):

**Table 5-1 Clinically notable laboratory abnormalities for selected tests**

HbA1c criteria is explicitly stated in the table below.

All other criteria are met when both of the following occur:

- Post-baseline values meet the thresholds below
- Baseline values or any previous post-baseline values do not meet the thresholds below

Parameters	Criteria
Hemoglobin	$\leq 10 \text{ g/dL}$
Hematocrit	$\leq 0.8 \times \text{LLN}$
WBC(total)	$\leq 2.8 \times 10^3 / \mu\text{L}$ , $\geq 16 \times 10^3 / \mu\text{L}$

Parameters	Criteria
Platelet count	$\leq 75 \times 10^3 / \mu\text{L}$ , $\geq 700 \times 10^3 / \mu\text{L}$
HbA1c	$\geq 6.5\%$ and $\geq 0.5\%$ increase from baseline
Creatinine	$> 2 \text{ mg/dL}$
CK	$> 1$ and $\leq 3 \times \text{ULN}$
CK	$> 3$ and $\leq 5 \times \text{ULN}$
CK	$> 5$ and $\leq 10 \times \text{ULN}$
CK	$> 10 \times \text{ULN}$

Notable liver function test criteria are defined in [Table 5-2](#).

**Table 5-2 Notable liver function test criteria**

**Peak post-baseline value**

---

ALT >3x ULN

ALT >5x ULN

ALT >10x ULN

ALT >20x ULN

---

AST >3x ULN

AST >5x ULN

AST >10x ULN

AST >20x ULN

---

ALT or AST >3x ULN

ALT or AST >5x ULN

ALT or AST >8x ULN

ALT or AST >10x ULN

ALT or AST >20x ULN

---

ALP > 2x ULN

---

Total bilirubin (BILI) >2x ULN

Total bilirubin (BILI) >3x ULN

---

**Combined elevations post-baseline**

For participants with AST and ALT <= ULN at baseline

Elevated ALT or AST (\$) & BILI >2x ULN

Elevated ALT or AST (\$) & BILI >2x ULN & ALP >=2x ULN

Elevated ALT or AST (\$) & BILI >2x ULN & ALP <2x ULN

---

For participants with ALT or AST > ULN at baseline

Elevated ALT or AST (\*) & BILI (>2x Bsl and 2x ULN)

Elevated ALT or AST (\*) & BILI (>2x Bsl and 2x ULN) & ALP >=2x ULN

Elevated ALT or AST (\*) & BILI (>2x Bsl and 2x ULN) & ALP <2x ULN

---

ALT = alanine aminotransferase, AST = aspartate aminotransferase, ALP = alkaline phosphatase

Combined elevations based on the peak post-baseline values (considering all post-baseline data from scheduled, unscheduled and premature discontinuation visit) for each parameter for each participant.

\* Elevated AST or ALT for participants with > ULN at baseline is defined as >3x Baseline or 8x ULN.

\$ Elevated AST or ALT for participants with <= ULN at baseline is defined as >3x ULN.

## 5.4 Statistical models

### 5.4.1 Analysis supporting primary objective(s)

#### 5.4.1.1 Primary efficacy analysis

In handling of intercurrent events and missing data not related to intercurrent events, multiple imputation will be used to account for uncertainty in the imputation process and there will be 100 multiply imputed datasets. The results from these 100 imputed datasets will be combined using Rubin's method. Further details are provided below.

For control-based PMM, the missing data after specific intercurrent events in inclisiran group will be imputed using data from control group. The covariates and baseline characteristics which can be predictive of the response will be included in a multiple imputation procedure (SAS PROC MI) and will include the following:

- Baseline value of efficacy measurement (continuous)
- Observed/imputed value of efficacy measurement at Day 30 (continuous)
- Observed/imputed value of efficacy measurement at Day 90 (continuous)
- Observed/imputed value of efficacy measurement at Day 150 (continuous)
- Observed/imputed value of efficacy measurement at Day 180 (continuous)

[figure not shown]
For RDO based imputation model, the missing data after treatment discontinuation will be imputed based on RDO data within each group. The covariates, baseline characteristics and on- or off- treatment status at the same visit with the response which can be predictive of the response will be included in a multiple imputation procedure (SAS PROC MI) and will include the following:

- Baseline value of efficacy measurement (continuous)
- Observed/imputed value of efficacy measurement at Day 30 (continuous)
- Observed/imputed value of efficacy measurement at Day 90 (continuous)
- Observed/imputed value of efficacy measurement at Day 150 (continuous)
- Indicator of on- or off- treatment status at Day 180 (binary)
- Observed/imputed value of efficacy measurement at Day 180 (continuous)

The indicator variable will vary with the imputed response from visit to visit.

1. For those participants who experienced the intercurrent event of using prohibited LLT, set the LDL-C values on or after the usage of LLT missing (out\_step1).
2. Missing data will be imputed under MAR assumption in this step. The same imputation model as specified for control-based PMM will be used except that the missing data will be multiply imputed using data within each treatment group. SAS PROC MI will be utilized using the FCS REG statement, where only previous measurements will be included for each imputed variable. A total of 100 datasets (out\_step2) will be created. These fully imputed datasets will be utilized in step 3.

3. For participants handled by intercurrent events of treatment discontinuation, if the measurement is missing in (out\_step1) and after treatment discontinuation, set this value back to missing (out\_step3). These datasets (out\_step3) will be utilized in step 4.
4. If there are enough RDO data, the RDO based imputation model will be used in this step. SAS PROC MI will be utilized using the FCS REG statement, where previous measurements and an indicator of on- or off-treatment status at the same visit with the response will be included for each imputed variable. This imputation will be implemented based on data within each group. If there are not enough RDO data, the control-based PMM will be used in this step. With this imputation model, the missing value in the inclisiran group will not be constructed from the observed data in the inclisiran group but rather from the observed and imputed data in the control group. SAS PROC MI will be utilized using the FCS REG statement, where only previous measurements will be included for each imputed variable. The MNAR statement in SAS PROC MI will also be used under MNAR assumption for inclisiran group. After this step, the 100 datasets(out\_step4) will be fully imputed. These datasets will be utilized in step 5. (Which model will be used in this step will be determined before Core Part database lock)
5. For participants who died, set the values after death using his/hers baseline value. (out\_step5)
6. Datasets (out\_step5) will be used in this step. The absolute change and the percentage change values will be calculated in each of the imputed datasets.
7. These 100 datasets will be analyzed using the ANCOVA model for the LDL-C endpoints.
8. The results from the 100 datasets will be combined using Rubin's method via SAS PROC MIANALYZE procedure.

#### 5.4.1.2 Supplementary analysis under estimand 1

The same imputation model as specified in [Appendix 5.4.1.1](#) will be used in supplementary analysis 1. Again, multiple imputation will be used to account for uncertainty in the imputation process and there will be 100 multiply imputed datasets. The results from these 100 imputed datasets will be combined using Rubin's method. Further details are provided below.

1. For those participants handled by any intercurrent event, set the LDL-C values on or after the intercurrent event missing (out\_step1).
2. Missing data will be imputed under MAR assumption in this step. The same imputation model as specified for control-based PMM will be used except that the missing data will be multiply imputed using data within each treatment group. SAS PROC MI will be utilized using the FCS REG statement, where only previous measurements will be

included for each imputed variable. A total of 100 datasets (out\_step2) will be created. These fully imputed datasets will be utilized in step 3.

3. The absolute change and the percentage change values will be calculated in each of the imputed datasets.
4. These 100 datasets will be analyzed using the ANCOVA model for the LDL-C endpoints.
5. The results from the 100 datasets will be combined using Rubin's method via SAS PROC MIANALYZE procedure.

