### 2.5.1 Primary endpoint(s)

The primary objective of this study is to demonstrate the superiority of inclisiran as monotherapy, compared to placebo, on mean percentage change from baseline in LDL-C at Day 150, in Chinese adults with low or moderate ASCVD risk and elevated LDL-C who are not on any lipid lowering therapy.

The primary endpoint is the percentage change from baseline at Day 150 in LDL-C.

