### 2.5.2 Statistical hypothesis, model, and method of analysis

The primary efficacy endpoint will be analyzed using an Analysis of Covariance (ANCOVA) model, in which the response variable will be the percentage change from baseline at Day 150 in LDL-C, treatment will be included as fixed-effect factor and baseline LDL-C will be included as a covariate.

The primary statistical hypothesis is stated as below.

- $H_0$ : the mean difference (inclisiran minus placebo) in percentage change from baseline at Day 150 in LDL-C is no less than zero.
- $H_1$ : the mean difference (inclisiran minus placebo) in percentage change from baseline at Day 150 in LDL-C is less than zero.

The study can be claimed a success if the null hypothesis ( $H_0$ ) is rejected at the one-sided significance level of 0.025.

The statistical test will be performed at the one-sided significance level of 0.025 based on the ANCOVA model. The estimate and the 95% confidence interval will be provided for the adjusted mean difference between inclisiran and placebo, and for the adjusted mean for both inclisiran and control groups, based on the ANCOVA model. The one-sided p-value will be provided for the primary null hypothesis.

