### 2.5.3 Handling of intercurrent events

The primary efficacy analysis will account for different intercurrent events as explained in the following:

- **Discontinuation of study treatment:** Retrieved drop out (RDO) data collected after discontinuation from study treatment will be used for the analysis (treatment policy). Missing data after discontinuation from study treatment will be multiply imputed based on RDO data within each treatment group, and when there are no sufficient RDO data, a control-based Pattern-Mixture Model (PMM) will be used for multiple imputation. In the PMM, missing not at random (MNAR) assumption will be used for inclisiran group. The detailed information is specified in [Appendix 5.4.1.1](#).
- **Use of prohibited LLT:** Use of prohibited LLT (PCSK9 monoclonal antibodies taken before Day 150 visit assessment or other LLT taken within 30 days before Day 150 visit assessment) will be treated in a hypothetical scenario of what would happen had those LLT not been taken, and those participants behaved like other participants in the same treatment group (hypothetical strategy). Data after those intercurrent events will be

excluded for the analysis and will be multiply imputed within each treatment group under MAR assumption.

- **Death:** Death due to CV or non-CV causes is considered as an unfavorable outcome (composite strategy). The LDL-C values at Day 150 after death will be set using the participant's baseline values.

In the case of multiple intercurrent events, death will be the dominant one in the analysis (if present). If a participant experiences only two other intercurrent events and usage of prohibited LLT occurs first, s/he will be handled by the event of usage of LLT (hypothetical strategy). If treatment discontinuation occurs prior to usage of prohibited LLT, then data after usage of LLT will be set missing and s/he will be handled by the event of treatment discontinuation (treatment policy). The detailed imputation model and algorithm are specified in [Appendix 5.4.1.1](#). Number and percentage of participants by each intercurrent event will be summarized by treatment group in core part analyses. Listing will also be provided.

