## 5.4.2 Analysis supporting secondary objective(s)

### Objectives for core part

The same imputation models and procedure as specified in [Appendix 5.4.1.1](#) will be applied to all secondary efficacy endpoints for core part. For Lp(a), log-transformation will be taken before the imputation and the imputation model will exclude variables at Day 30 and Day 90 visits.

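### A missed Day 150 value is imputed from earlier visits only, so an observed, usable Day 180 value does not inform the primary endpoint (for Lp(a), baseline alone does)

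*SAP*

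**What the plan says.** The primary endpoint is fixed at one visit: "The primary endpoint is the percentage change from baseline at Day 150 in LDL-C" (SAP 2.5.1). Appendix 5.4.1.1 gives two variable lists, one for the control-based pattern-mixture model and one for the model based on retrieved drop-out (RDO) data. Both end with "Observed/imputed value of efficacy measurement at Day 180 (continuous").

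The steps then limit what predicts what:

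- Step 2 (MAR, within arm) uses FCS regression "where only previous measurements will be included for each imputed variable".
- Step 4 repeats this limit for the control-based model. Its RDO version uses previous measurements plus the same-visit on- or off-treatment indicator.
- SAP 5.4.2 applies the same procedure to the core-part secondary endpoints. For Lp(a) it adds that "the imputation model will exclude variables at Day 30 and Day 90 visits".
- SAP 2.5.3 says of treatment discontinuation: "Retrieved drop out (RDO) data collected after discontinuation from study treatment will be used for the analysis (treatment policy").

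**The concern.** Protocol 1.3 says that a missed visit should not lead to automatic discontinuation, and that participants who stop treatment keep attending. A participant can therefore miss Day 150 and attend Day 180. The same section puts all assessments before dosing at treatment visits. The Day 90 sample thus reflects the first dose only, while the Day 180 sample follows both core doses and precedes the switch. It is 30 days from Day 150, against 60 days for Day 90.

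Leaving it out has two consequences. Imputed values are noisier than they need be. The MAR assumption must also hold given baseline, Day 30 and Day 90 alone, rather than given those and Day 180. No planned analysis tests this choice: the tipping-point analysis in SAP 2.5.5 concerns prohibited therapy only, and both supplementary analyses (5.4.1.2 and 5.4.1.3) keep the earlier-visits rule.

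**Working it through.** **Which variables reach Day 150.**

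| Branch | Predictors of a missing Day 150 value |
|---|---|
| Step 2, MAR | baseline, Day 30, Day 90 |
| Step 4, control-based | baseline, Day 30, Day 90 |
| Step 4, RDO | baseline, Day 30, Day 90, Day 150 on/off indicator |
| Lp(a) | baseline (plus the indicator under RDO) |

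Step 3 only resets values to missing and step 5 concerns deaths, so nothing feeds Day 180 back.

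**Who is affected.** Participants with Day 150 missing and a usable Day 180. After prohibited therapy, later values are set to missing. After death, the baseline value is used. An early-exit sample following Day 90 is mapped to Day 150 (SAP Table 2-1) and needs no imputation.

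**The plan's own figure.** "This study is designed to randomize approximately 200 Participants (with randomization ratio of 1:1 to inclisiran and placebo arms"), "as well as to have sufficient power for the primary efficacy endpoint" (SAP 3). The published text gives no effect, SD or power, so 200 cannot be reproduced. For scale, at one-sided 0.025 and 100 per arm, 90% power needs (1.960 + 1.282) × √(2/100) = 0.458 SD. With an assumed difference of 30 points and SD of 30, the least favourable pair tried (differences 30 to 50, SDs 15 to 30), the expected z is 30/(30 × √0.02) = 7.07. Power is about 100% throughout.

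**Residual variance of Day 150 (total = 1).** The documents give no correlations, so two structures are assumed.

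- Equal correlation ρ between visits: with k predictors, residual = 1 − kρ²/(1 + (k − 1)ρ). For LDL-C, k goes from 3 to 4. For Lp(a), k goes from 1 to 2. Example, ρ = 0.6, LDL-C: 1 − 1.08/2.2 = 0.509, then 1 − 1.44/2.8 = 0.486.
- Decaying correlation ρ^(gap/60 days): residual = 1 − a without Day 180 and (1 − a)(1 − b)/(1 − ab) with it. Here a is the squared correlation with the last earlier visit (ρ² for Day 90; ρ^(298/60) for Day 1), and b = ρ is the squared correlation with Day 180. Example, ρ = 0.8, LDL-C: 0.360, then 0.36 × 0.2/(1 − 0.512) = 0.148.

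| Structure, ρ | LDL-C: plan, with Day 180 | Cut | Lp(a): plan, with Day 180 | Cut |
|---|---|---|---|---|
| Equal, 0.4 | 0.733, 0.709 | 3% | 0.840, 0.771 | 8% |
| Equal, 0.6 | 0.509, 0.486 | 5% | 0.640, 0.550 | 14% |
| Equal, 0.8 | 0.262, 0.247 | 6% | 0.360, 0.289 | 20% |
| Decaying, 0.4 | 0.840, 0.538 | 36% | 0.989, 0.596 | 40% |
| Decaying, 0.6 | 0.640, 0.327 | 49% | 0.921, 0.387 | 58% |
| Decaying, 0.8 | 0.360, 0.148 | 59% | 0.670, 0.182 | 73% |

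**Effect on the standard error (SE) of the treatment difference.** If a fraction f is missing at random and every such participant has Day 180, the variance is inflated by about 1 + v·f/(1 − f). Here v is the residual variance above divided by the residual variance given baseline alone, because ANCOVA already adjusts for baseline. For LDL-C, decaying, ρ = 0.6, f = 0.10:

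- Plan: v = 0.640/0.921 = 0.695, inflation 1.077.
- With Day 180: v = 0.327/0.921 = 0.355, inflation 1.039.
- SE falls by 1 − √(1.039/1.077) = 1.8%.

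Across the table at f = 0.10, the LDL-C gain is 0.1% to 1.8%. For Lp(a), v = 1 under the plan and the gain is 0.4% to 3.7%.

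A simulation agrees (400 trials, 100 per arm, 20 imputations, SD 20, true difference −50, decaying correlation):

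| Missing at random | ρ | SE, plan | SE, with Day 180 | Fall |
|---|---|---|---|---|
| 3% | 0.5 | 2.859 | 2.844 | 0.5% |
| 3% | 0.8 | 2.851 | 2.839 | 0.4% |
| 10% | 0.5 | 2.978 | 2.920 | 1.9% |
| 10% | 0.8 | 2.900 | 2.863 | 1.3% |

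**If missingness depends on the Day 180 level.** Suppose that in the inclisiran arm the log-odds of missing Day 150 rise by 1.5 per SD of the Day 180 residual, starting from 5% or 10% at the average. Averaged over a normal distribution, that is about 10% or 17% missing in that arm. Bias is the estimate minus the complete-data estimate:

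| Start | ρ | Plan | With Day 180 |
|---|---|---|---|
| 5% | 0.5 | −51.54 + 50.16 = −1.38 | −0.06 |
| 10% | 0.5 | −51.86 + 49.87 = −1.99 | +0.10 |
| 5% | 0.8 | −50.97 + 50.16 = −0.81 | +0.04 |
| 10% | 0.8 | −51.35 + 50.00 = −1.35 | −0.02 |

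The plan overstates the effect by 0.8 to 2.0 points on about −50. With Day 180 the bias is 0.1 point or less.

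**The case against.** The strongest reply is that this is a sound sequential imputation, each visit drawn from earlier ones, and that the alternative buys little. Most of that stands. Few participants are likely to be affected, although the documents give no rate of missed visits. Under equal correlation, Day 180 adds only about 0.02 to the explained variance of LDL-C. The bias scenario is a stress test. Participants, investigators and site staff are blinded to lipid results and are told not to obtain them locally (Protocol 8.3.1, 8.3.2), so the documents give no reason to expect missed visits to follow lipid levels. Lp(a) is a secondary endpoint with nominal p-values only.

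Two stronger readings are tempting, and the documents support neither. A reader might infer that listing Day 180 while barring it as a predictor is a contradiction. It is not: Day 180 is the last variable in the chain and is itself imputed from the others. A reader might also infer that SAP 2.5.3 is breached when a discontinuer's Day 180 value is not used. That section commits to using retrieved data and to imputing from them within arm. It does not promise that a participant's own Day 180 value will predict that participant's Day 150 value.

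The reply leaves one thing unanswered: in the MAR step, an observed and relevant value is ignored for no stated reason.

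**Conclusion.** The point holds as a minor improvement. In every branch a missing Day 150 value is imputed without an observed Day 180 value, and for Lp(a) no post-baseline measurement contributes. Under the assumed correlations and 3% to 10% missing at random, the cost to the primary comparison is about 2% of the standard error or less, and relatively more for Lp(a).

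The superiority conclusion is not at stake. In the least favourable case above, an SE larger by 2% moves z from 7.07 to 7.07/1.02 = 6.93, and removing a 2-point bias leaves (30 − 2)/4.24 = 6.6, against a critical value of 1.96 for a test specified as "The statistical test will be performed at the one-sided significance level of 0.025 based on the ANCOVA model".

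The requirement that MAR hold without Day 180 could shift the estimate by 1 to 2 points, but only under a mechanism that the documents give no reason to expect. Correlations, SD, effect and missing rates are all assumptions. The trace through the steps is not.

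**What to change.** 1. In step 2 of SAP 5.4.1.1, and in the same MAR step for Lp(a) and the other core-part secondary endpoints, let the FCS regression for Day 150 also condition on Day 180.
2. Define a usable Day 180 value as one taken before the Day 180 dose and free of prohibited therapy. The intercurrent event is dated relative to Day 150, so state that Day 180 values after therapy begun between Day 150 and Day 180 are also set to missing for this purpose.
3. Leave the step 4 RDO and control-based models as they are. The same-visit indicator and the MNAR statement make a change there more than a one-line edit. For treatment discontinuers with an observed Day 180 value but no Day 150 value, condition on that value in a sensitivity analysis.
4. Report by arm how many participants lack Day 150 but have a usable Day 180.

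The cost is one SAP clause, a revised Day 150 regression in the code, a stated burn-in (the chain is no longer strictly sequential) and one sensitivity analysis. No new data are needed.

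Timing matters. The SAP history labels Amendment 1 as prior to core-part lock and Amendment 2 (21 August 2024) as prior to final lock, so the core database may already be locked. If it is, keep the prespecified primary analysis and report items 1 to 3 together as a labelled sensitivity analysis.
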